2.2.1.2 Clinical Pharmacokinetics (PK) and Activity of Trametinib

FTIH Phase 1 Trial of Trametinib Monotherapy (MEK111054): There were 3 parts in this study.

- Part 1: The dose-escalation portion involves administration of trametinib (repeat doses of 0.125 mg to 4.0 mg) to patients with solid tumors or lymphoma in one of three schedules - (1) QD for 21 days followed by 7 days without drug, (2) loading dose on Day 1 or Day 1-2, followed by QD with the designated dose, or (3) QD dosing without a drug holiday.
- Part 2: Cohort expansion at the recommended phase 2 dose (RP2D) for pancreatic cancer, melanoma, NSCLC, CRC, or any BRAF mutation-positive cancer.
- Part 3: Expansion to characterize the biologically active range of trametinib via analysis of pharmacodynamic biomarkers (biopsies or FDG-PET).

The MTD of trametinib was established as 3 mg QD, but the recommended phase 2 dose (RP2D) was chosen at 2 mg QD based on tolerability of repeated cycles.³¹

PK and Metabolism of Trametinib: PK measurements were conducted under fasting conditions. After a single dose (Day 1), AUC_{0-24} and C_{\max} values were dose-proportional up to 6 mg, lower than dose proportional following 8 mg, and greater than dose proportional following the 10 mg dose. Median T_{\max} was 1.5 hours.

After repeat doses (Day 15), trametinib accumulated with a mean accumulation ratio of 6.6 at the RP2D of 2 mg QD. Between-subject variability in exposure ranged from 27-50% for C_{\max} and 20-41% for AUC_{0-24} across all dosing regimens. The effective $t_{1/2}$ was approximately 4.5 days, and steady state was reached by approximately Day 15. Trametinib had a small peak:trough ratio of ~2.³¹ At 2 mg QD on Day 15, mean AUC_{0-24} was 376 ng•h/mL and C_{\max} 23 ng/mL, and the mean trough concentrations ranged from 10.0 to 18.9 ng/mL. The long half life and small peak:trough ratio of trametinib allowed constant target inhibition within a narrow range of exposure.

Drug-Drug Interactions: Trametinib is metabolized predominantly via deacetylation (non-cytochrome P450 [CYP450]-mediated) with secondary oxidation or in combination with glucuronidation biotransformation pathways.³⁰ The deacetylation is likely mediated by hydrolytic esterases, such as carboxylesterases, or amidases. Based on in vitro studies, trametinib is not an inhibitor of CYP1A2, CYP2A6, CYP2B6, CYP2D6, and CYP3A4. Trametinib has an overall low potential for drug-drug interactions.

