In collaboration with investigators at the Institut Curie, Paris France, MSK, and/or Columbia, we propose to prospectively measure ctdDNA in patients with metastatic uveal melanoma. The primary objective is to describe the evolution of ctdDNA levels measured by PAP in plasma of patients under treatment for metastatic uveal melanoma. Additionally, we will evaluate the early changes of circulating tumor DNA levels as early indicator of efficiency or non-efficiency of treatment and correlate circulating DNA levels with tumor imaging of metastases. Patients on this study at MSK will be required to submit peripheral blood samples prior to treatment, at various time points on treatment, and at progression.

All patients will undergo blood collection on a monthly basis for analysis of circulating tumor DNA levels. Using a real-time PCR developed based on bi-directional pyrophosphorolysis-activated polymerization (bi-PAP) for the quantification of ctDNA using 3'blocked primer pairs specific for the 3 recurrent mutually exclusive mutations of G α subunits Gnaq and Gnal1, Madic et. al. have been able to detect and quantify circulating tumor DNA in metastatic UM patients.⁶¹ We will utilize this assay to measure circulating tumor DNA and correlate changes in DNA levels with response to treatment.

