9.2.3 Circulating Tumor DNA Plasma Collection

Two 10 cc lavender top tube (EDTA) will be collected prior to treatment, at the beginning of each cycle, and at the End of Treatment visit. The samples drawn prior to treatment can be drawn on C1W1 prior to initiation of study drug.

Plasma samples should be prepared as described by Diehl et. al. and as summarized [below](#).⁶⁵

1. Within 1 hour of collection, blood is centrifuged at 820 g for 10 minutes.
2. Supernatant is transferred to 1.5 mL sterile tubes in 1 mL aliquots and centrifuged at 16,000g for 10 minutes at 4°C to pellet any remaining cellular debris. Discard the pellet.
3. Label tubes with the subject's study identification number, the date of collection, time point (baseline, cycle number, or end of study) and the study center. MSK patients will be identified by accession number.
4. The supernatant should subsequently be stored at -80°C.
5. The overall process from blood collection to plasma storage should not exceed 3 hours.
6. The supernatant will be shipped from each investigational site directly to the Institut Curie.

DNA extraction will be performed at the Institut Curie as follows:

1. DNA extraction from plasma of patients should be accomplished using the Qiagen QIAamp circulating nucleic acid kits or an acceptable alternative. Extraction should be performed according to the manufacturer instructions.
2. Nucleic acids should be stored at -20°C.

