10 STUDY CALENDAR

Baseline evaluations are to be conducted within 14 days prior to start of protocol therapy. Imaging studies and cardiac evaluation (e.g., echocardiogram, MUGA, EKG) must be done ≤ 4 weeks prior to the start of therapy. The pre-treatment biopsy for patients with safely accessible tumor will be obtained within 28 days of starting therapy (see [Section 9.2.1](#) for more information). In the event that the patient's condition is deteriorating, laboratory evaluations should be repeated within 48 hours prior to initiation of therapy. All blood work, examinations and procedures may be performed +/- 3 days from the scheduled date. Imaging studies may be performed +/- 1 week from the scheduled date.

		Cycle 1				Cycle 2				Cycle 3 ^m				
	Pre-Study	Wk 1	Wk 2	Wk 3	Wk 4	Wk 5	Wk 6	Wk 7	Wk 8	Wk 9	Wk 10	Wk 11	Wk 12	End of Treatment ⁿ
Trametinib (Arms A or B)		X-----X												
GSK2141795 (Arm B Only)		X-----X												
Informed consent	X													
Demographics	X													
Medical history	X													
Concurrent meds	X	X-----X												
Physical exam	X	X		X		X				X				X
Ophthalmology Exam ^a	X ^a													
Vital signs ^b	X ^b	X		X		X				X				X
Height	X													
Weight	X	X		X		X				X				X
Performance status	X	X		X		X				X				X
CBC w/diff, plts	X	X	X ^o	X	X ^o	X				X				X
Chemistries ^c	X	X	X ^o	X	X ^o	X				X				X
PT/PTT	X													
Fasting Lipid Panel ^d	X									X				X
Fasting Glucose	X													
Hemoglobin A1c ^d	X									X				X
TSH ^d	X									X				X
EKG ^e	X			X		X				X				X
Echocardiogram or MUGA ^f	X					X								X
Adverse event evaluation		X-----X												X

CAP CT or Chest CT and AP MRI ^g	X	Tumor measurements are repeated every 8 weeks.										X
B-HCG ^h	X											
Archived Tumor Tissue ⁱ	X											
Tumor Biopsy ^j	X			X								(X)
Research Blood Collection ^k		X				X				X		X
ctDNA Blood Collection ^l		X				X				X		X

- a: Ophthalmic exam will include indirect funduscopy, slit lamp exam, visual acuity, visual field examination, tonometry and color fundus photos. Additional ophthalmic exams will be performed if symptomatically warranted. Note that patients with the presence at baseline of a risk factor for RVO or REPD such as evidence of new optic disc cupping, evidence of new visual field defects, and intraocular pressure >21 mm Hg are excluded from this trial.

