- b: Patients with treatment-refractory hypertension defined as a blood pressure of systolic >140 mmHg and/or diastolic >90 mmHg which cannot be controlled by anti-hypertensive therapy are excluded from this trial.
- c: Albumin, alkaline phosphatase, total bilirubin, bicarbonate, BUN, calcium, chloride, creatinine, glucose, LDH, phosphorus, potassium, total protein, SGOT [AST], SGPT [ALT], sodium.
- d: Repeat test every 8 weeks.
- e: A single 12-lead ECG should be performed at Screening, Day 15, and prior to dosing at the start of every 4 weeks. The baseline EKG may be conducted within 28 days of treatment start date. Additional EKGs will be performed as clinically indicated. Patients with a baseline QT interval corrected for heart rate using the Bazett's formula QTcB ≥ 480 msec are excluded from this trial.
- f: Echocardiogram or MUGA should be performed at screening, Week 5 Day 1, then every 12 weeks, at final study visit, and as clinically indicated. The same methodology should be used throughout the study.
- g: CT of the chest, abdomen and pelvis with contrast OR CT of the chest (with or without contrast) and MRI of the abdomen and pelvis at baseline and again every subsequent 8 weeks (+/- 1 week). Other imaging modalities can be used in addition to these at the discretion of the treating physician. If the patient is taken off treatment for any reason other than disease progression, End of Treatment imaging is not required at that visit; however, the patient should undergo restaging scans 8 weeks (+/- 1 week) from the time of the first dose and continue having scans every 8 weeks (+/- 1 week) until progression is documented, the start of new anticancer therapy, or death.
- h: Perform only in women of child-bearing potential. A blood pregnancy test should be performed at Screening, and subsequent pregnancy tests may be either blood or urine.
- i: Up to twenty unstained slides from archived or newly acquired paraffin embedded tumor or the tumor block will be collected from all patients enrolled on this study.
- j: Tumor biopsies will be performed at baseline and after 14 +/- 3 days of therapy. A third optional tumor biopsy may be performed on these patients at the time of disease progression.

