- k: Serum will be collected from patients as outlined in [Section 9](#) prior to treatment, at the beginning of each cycle, and at the off-study visit and subsequently stored for future correlative studies. The samples drawn prior to treatment can be drawn on C1W1 prior to initiation of study drug.
- l: Two 10 cc lavender top tube (EDTA) will be collected prior to treatment, at the beginning of each cycle, and at the End of Treatment visit. The samples drawn prior to treatment can be drawn on C1W1 prior to initiation of study drug.
- m: Cycle 4+ will be conducted as indicated for cycle 3.
- n: End of Treatment Visit performed 4 weeks from last treatment. Patients will be contacted or evaluated every 12 weeks (+/- 1 week) for survival assessment after End of Treatment visit or last date of follow up. In the event that the patient's health deteriorates such that the follow-up visit is not feasible, a note will be placed in the subject's medical record documenting the situation. This will not be considered a protocol violation. In addition, the last treatment visit can be considered the End of Treatment visit if the patient is unable to return, a note will be placed in the subject's medical record documenting this situation.
- o: Test can be performed locally.

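### No ctDNA draw is scheduled at progression: the closing draw comes 4 weeks after the last dose and does not match the scan that dates progression

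*Combined protocol and SAP*

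**What the plan says.** **Intent.** Section 2.4.3 requires patients at the lead center to give blood "prior to treatment, at various time points on treatment, and at progression". The same section plans to follow ctDNA levels over treatment, to test early changes as an indicator of treatment effect, and to correlate levels with imaging of metastases.

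**Schedule.** Section 9.2.3 and Study Calendar footnote l give the ctDNA draws as one before treatment, then "at the beginning of each cycle, and at the End of Treatment visit". Section 9.2.4 uses the same three time points for exosomal and proteomic plasma. Neither section names a progression draw.

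**Date of the closing visit.** Footnote n: "End of Treatment Visit performed 4 weeks from last treatment". The calendar preamble adds a window: "All blood work, examinations and procedures may be performed +/- 3 days from the scheduled date". Footnote n also has an exception: "the last treatment visit can be considered the End of Treatment visit if the patient is unable to return".

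**Related items.**
- The calendar marks the optional third biopsy (X) only in the End of Treatment column, but footnote j to that row says "A third optional tumor biopsy may be performed on these patients at the time of disease progression".
- Section 9.2.2 and footnote k place the closing research blood at an off-study visit. That visit is not defined, and the calendar mark is again in the End of Treatment column.

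**The concern.** The background section promises a sample at progression, and the sections that sites work from do not deliver one. The nearest scheduled sample is set by the last dose, not by the scan. Section 2.4.3 wants ctDNA set against imaging, and Section 2.4.3's companion text in the same part of the protocol treats tumor volume as a major determinant of ctDNA. Four further weeks without study drug can change tumor volume, so the closing value may not describe the tumor that met the progression criteria.

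The closing samples will also be mixed. Some will come from the 4-week visit, and some from the last treatment visit under the footnote n exception. Section 13.5 plans only to assess whether ctDNA is detectable and to summarize it by clinical response. It gives no rule for separating samples taken on drug from samples taken off drug.

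**Working it through.** The protocol states no figure on this point to reproduce. The check has two parts: where the draws fall relative to the scan, and how much drug remains at the closing visit.

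**1. Draws around a progression scan**

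Inputs from the Study Calendar: 4-week cycles with a draw at each cycle start (±3 days); scans every 8 weeks (±7 days). The week 8 scan is taken as day 57, which is also Cycle 3 Day 1. Cycle 2 Day 1 is day 29.

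- If Cycle 3 starts, that draw and the scan are at most 7 + 3 = 10 days apart.
- If Cycle 3 does not start, the last on-drug draw is 57 − 29 = 28 days before the scan. Over the windows the gap runs from (57 − 7) − (29 + 3) = 18 to (57 + 7) − (29 − 3) = 38 days.
- The closing draw is 28 days after the last dose (25 to 31). If the last dose is on the scan day, that is day 57 + 28 = 85.

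Scans recur every second cycle, so the nominal spacing is the same at every later scan.

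**2. Drug remaining at the closing visit**

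Fraction of steady state left = 2^(−t / half-life), assuming first-order decline at the stated effective half-lives.

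For trametinib, Section 2.2.1.2 gives a half-life that "was approximately 4.5 days, and steady state was reached by approximately Day 15". For GSK2141795, Section 2.2.2.2 gives a mean of 3.0 days and a range of about 1.3 to 5.5 days.

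| Agent | Half-life (days) | Half-lives in 28 days | Left at 28 days | Left at 25 to 31 days |
|---|---|---|---|---|
| Trametinib | 4.5 | 6.2 | 1.3% | 2.1% to 0.8% |
| GSK2141795, mean | 3.0 | 9.3 | 0.16% | 0.31% to 0.08% |
| GSK2141795, longest | 5.5 | 5.1 | 2.9% | 4.3% to 2.0% |

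Check on the trametinib input: the stated accumulation ratio of 6.6 with daily dosing implies a half-life of ln 2 / (−ln(1 − 1/6.6)) = 4.2 days, close to 4.5, and would leave 1.0% at 28 days. On the concentration scale, day 15 mean troughs of 10.0 to 18.9 ng/mL at 2 mg fall to 10.0 × 0.0134 = 0.13 and 18.9 × 0.0134 = 0.25 ng/mL.

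**3. How many patients this could touch at the first scan**

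With exponential PFS and the 16-week median of Section 13.1, 1 − 0.5^(8/16) = 29% have an event by week 8. This is illustrative only. It counts deaths, which yield no progression draw, and it says nothing about whether the Cycle 3 draw is made. For those who progress then and have no Cycle 3 draw, Cycle 2 Day 1 is the only on-drug ctDNA value.

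**The case against.** **The gap can close in practice.** A cycle-start draw falls due at each scan, and nothing says the scan result comes first or that the draw is then skipped. Section 5.3 allows treatment beyond progression with approval. Footnote n lets the last treatment visit stand in for End of Treatment. All of this stands, so the gap is conditional on the next cycle not being started. It does not remove the point, because no text makes a progression draw due.

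**There is an End of Treatment scan to pair with.** Footnote g waives imaging at that visit only for patients stopping for reasons other than progression, so progressors can have a scan beside the closing draw. This also stands, but that scan is not the one that dates progression. Loss of drug does matter less for a measure of tumor burden than for a pharmacodynamic marker.

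**Little is left to move.** Arm B and crossover are closed to enrolment, and Section 5.1 requires all patients to be off treatment by March 31, 2017. A change of schedule now reaches few patients. The analysis rule can still reach every sample already collected.

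**Stronger readings that the documents do not support.**
- A reader might infer from the (X) that the progression biopsy is taken after washout, so that returning pERK, pAKT or cyclin D1 would be misread as resistance. Footnote j, the Schema and Sections 2.4.2, 9.1 and 9.2.1 all place that biopsy at progression. Sections 9.4.2 and 13.5 plan the marker comparison as baseline against day 14. The grid is ambiguous, but nothing instructs an off-drug biopsy.
- A reader might conclude that the samples cannot show an on-drug resistant state. Cycle-start draws are on drug, and Section 1.3 names primary resistance only, although Section 9.2.1 does seek biopsies at progression after response or prolonged control.
- Research blood is never described as a progression sample.
- The sentence in Section 5.1 allowing any later therapy sits in the text on crossover patients. It is not a general statement about the weeks before End of Treatment.

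**Conclusion.** The point holds for ctDNA blood. Section 2.4.3 calls for a sample at progression, and Section 9.2.3 with footnotes l and n schedules none. When the next cycle is not started, the nearest draws are about 4 weeks before the scan (18 to 38 days over the windows) and about 4 weeks after the last dose, with study drug almost cleared. The sizes rest on first-order decline at the stated effective half-lives; terminal half-lives are not given, and longer ones would leave more drug. The biopsy mark and the off-study visit are matters of wording to reconcile. The primary endpoint, the secondary endpoints and safety are unaffected.

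**What to change.** 1. In Sections 9.2.3 and 9.2.4 and footnote l, for patients stopping for progression, take the closing draw at the visit where progression is documented instead of at the 4-week visit. A workable window is within 7 days of the progression scan and before any new anticancer therapy.
2. In Section 13.5, derive days since last dose for each closing sample from the medication diary (Section 5.1, Appendix F) and the collection date on the tube label. Analyse on-drug and off-drug closing samples separately. This needs no new data item and also covers samples already collected.
3. Add a Progression column to the calendar and move the optional biopsy (X) into it, in line with footnote j.
4. In Section 9.2.2 and footnote k, state whether the off-study visit means the progression visit or the End of Treatment visit.

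The cost is an amendment to wording and calendar. The number of draws and biopsies stays the same, and the rules for stopping treatment are untouched. What is lost is the 4-week post-treatment blood point in progressors. If the change is made late, the closing samples will carry two timings, which step 2 handles.

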11 MEASUREMENT OF EFFECT

11.1 Antitumor Effect – Solid Tumors

For the purposes of this study, patients should be re-evaluated for response every 8 weeks. As per RECIST 1.1, confirmatory scans obtained 4 weeks following initial documentation of objective response is not necessary in this study where the primary endpoint is PFS. Patients will be re-evaluated for response until progression is documented, the start of new anticancer therapy, or death.

Response and progression will be evaluated in this study using the new international criteria proposed by the revised Response Evaluation Criteria in Solid Tumors (RECIST) guideline (version 1.1).⁶⁶ Changes in the largest diameter (unidimensional measurement) of the tumor lesions and the shortest diameter in the case of malignant lymph nodes are used in the RECIST criteria.

11.1.1 Definitions

Evaluable for toxicity. All patients will be evaluable for toxicity from the time of their first treatment with trametinib alone or with GSK2141795.

Evaluable for objective response. Only those patients who have measurable disease present at baseline, have received at least one cycle of therapy, and have had their disease re-evaluated will be considered evaluable for response. These patients will have their response classified according to the definitions stated [below](#). (Note: Patients who exhibit objective disease progression prior to the end of cycle 1 will also be considered evaluable.)

Evaluable Non-Target Disease Response. Patients who have lesions present at baseline that are evaluable but do not meet the definitions of measurable disease, have received at least one cycle of therapy, and have had their disease re-evaluated will be considered evaluable for non-target disease. The response assessment is based on the presence, absence, or unequivocal progression of the lesions.

11.1.2 Disease Parameters

Measurable disease. Measurable lesions are defined as those that can be accurately measured in at least one dimension (longest diameter to be recorded) as ≥ 20 mm by chest x-ray or as ≥ 10 mm with CT scan, MRI, or calipers by clinical exam. All tumor measurements must be recorded in millimeters (or decimal fractions of centimeters).

Note: Lesions that are previously irradiated must show clear evidence of progression over a minimum of 3 months to include as measurable. This period of time is used to discount tumor edema in an irradiated field as a false sign of disease progression.

Malignant lymph nodes. To be considered pathologically enlarged and measurable, a lymph node must be ≥ 15 mm in short axis when assessed by CT scan (CT scan slice thickness recommended to be no greater than 5 mm). At baseline and in follow-up, only the short axis will be measured and followed.

Non-measurable disease. All other lesions (or sites of disease), including small lesions (longest diameter < 10 mm or pathological lymph nodes with ≥ 10 to < 15 mm short axis), are considered non-measurable disease. Bone lesions, leptomeningeal disease, ascites, pleural/pericardial effusions, lymphangitis cutis/pulmonitis, inflammatory breast disease, and abdominal masses (not followed by CT or MRI), are considered as non-measurable.

Note: Cystic lesions that meet the criteria for radiographically defined simple cysts should not be considered as malignant lesions (neither measurable nor non-measurable) since they are, by definition, simple cysts.

‘Cystic lesions’ thought to represent cystic metastases can be considered as measurable lesions, if they meet the definition of measurability described above. However, if non-cystic lesions are present in the same patient, these are preferred for selection as target lesions.

Target lesions. All measurable lesions up to a maximum of 2 lesions per organ and 5 lesions in total, representative of all involved organs, should be identified as **target lesions** and recorded and measured at baseline. Target lesions should be selected on the basis of their size (lesions with the longest diameter), be representative of all involved organs, but in addition should be those that lend themselves to reproducible repeated measurements. It may be the case that, on occasion, the largest lesion does not lend itself to reproducible measurement in which circumstance the next largest lesion which can be measured reproducibly should be selected. A sum of the diameters (longest for non-nodal lesions, short axis for nodal lesions) for all target lesions will be calculated and reported as the baseline sum diameters. If lymph nodes are to be included in the sum, then only the short axis is added into the sum. The baseline sum diameters will be used as reference to further characterize any objective tumor regression in the measurable dimension of the disease.

Non-target lesions. All other lesions (or sites of disease) including any measurable lesions over and above the 5 target lesions should be identified as **non-target lesions** and should also be recorded at baseline. Measurements of these lesions are not required, but the presence, absence, or in rare cases unequivocal progression of each should be noted throughout follow-up.

